15.2 Secondary endpoints

Secondary endpoints of efficacy are to evaluate overall survival, progression-free survival and response rates. The overall survival and progression-free survival will be estimated using the Kaplan-Meier method, and Greenwood's formula will be used to calculate the standard error of the corresponding Kaplan-Meier estimate and 95% confidence interval. Survival curves will be estimated using Kaplan-Meier methodology. Response rates will be calculated as described in section 13.4. Accrual is expected to take 2 years with a minimum of 1 year subsequent follow-up, overall follow-up will range from 1 to 3 years.

Other secondary objectives will include description of toxicity of the therapy regimen. These data will be analyzed separately. The safety analyses will be performed on all patients who receive any dose of therapy. Adverse events will be described using the NCI CTCAE v 4.0 criteria (ctep.cancer.gov/forms/CTCAEv4.pdf). Frequency and severity of adverse events according to the NCI CTCAE v# body system and severity criteria will be described. In addition, frequency of Grade 3 or 4 adverse events will be described separately. Causality will also be noted. Adverse events will be recorded for up to 1 year following discontinuation from study.

Laboratory assessments will also be described according to the NCI CTCAE v 4 criteria, with separate descriptions for Grade 3 or 4 laboratory abnormalities. Clinically significant laboratory abnormalities will be described as well. Serious adverse events will be summarized, including a causality assessment.

The number of treatment cycles and doses administered will be summarized using descriptive statistics. Treatment delays will be summarized using counts and percentages.

Patients' disposition will be summarized in the following manner:

- The number and percentage of patients selected, included, completed, withdrawn and lost to follow-up will be summarized using descriptive statistics.
- Major protocol deviations will be summarized.
- The reason for withdrawal (adverse events, lack of efficacy, major protocol deviation, non-medical reason, recovery or remission) will be summarized.

For pathology-, laboratory- and imaging-correlative studies, Cox regression analysis will be conducted to investigate the association between TTP and parameters from correlative studies.

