Another non-IND phase 2 study is being conducted in untreated locally advanced or metastatic NSCLC to investigate the safety and efficacy of bavituximab 3 mg/kg weekly in combination with carboplatin plus paclitaxel in 21-day cycles. Twenty of 49 patients experienced AEs considered related to bavituximab, including anemia and fatigue, and 8 patients experienced drug-related SAEs, which included fatal myocardial infarction (in 2 patients) and fatal hemoptysis and aspiration (in 1 patient). Among stage A patients (in a Simon 2-stage design) in the ITT group, the ORR was 52% (11/21). Grade 3 or 4 AEs were experienced by 28.5% of patients. The most common grade 3 or 4 AEs were anemia (4 patients), asthenia (4 patients) and neutropenia (4 patients). (29)

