11.0 DOSE-LIMITING TOXICITIES-PHASE I COMPONENT

The phase I component of the study will consist of a traditional 3+3 dose escalation rule with the dose of sorafenib remaining constant and the dose of bavituximab escalating up to 3.0 mg/kg weekly to determine the maximum tolerated dose (MTD) that will be used during the phase II component. Sorafenib has been demonstrated in multiple phase I and II studies in advanced HCC to have minimal toxicity and to be safe, therefore doses will be constant. (13,14) Cohorts of three patients will be assigned to one dose level of bavituximab starting at 0.3 mg/kg weekly. Only the first cycle of therapy (4 doses of bavituximab and 4 weeks of sorafenib constitutes a cycle) will be used to determine dose limiting toxicity (DLT). The patients will be followed for thirty days following the end of the first cycle for adverse events. These adverse events will be submitted to the Data Safety Monitoring Committee for evaluation. During this thirty-day period and beyond patients will be administered sorafenib at the discretion of the treating oncologist. Patients will be enrolled into the next highest drug cohort only after 3 or 6 patients have completed the first cycle of therapy. The number of observed toxicities is counted and the traditional escalation rule applied:

- No toxicity: the next three patients will be assigned to next higher dose level (3.0 mg/kg of bavituximab is the highest dose assigned).
- At least two toxicities: the MTD is exceeded and the phase I component of the trial will be stopped with the next lowest dose to be defined as the MTD that will be used in the phase II component.
- One toxicity: the cohort will be expanded to 6 patients.
 - One DLT within the last six patients: The next cohort of three patients will be assigned to the next highest dose level
 - At least two DLTs within the last six patients: the MTD is exceeded and the phase I component of the trial will be stopped with the next lowest dose to be defined as the dose that will be used in the phase II component.

The Data and Safety Monitoring Committee and investigators as described below will regularly review all adverse events. The study will utilize the Common Terminology Criteria for Adverse Events (CTCAE) version 4.0 for grading of all adverse events related to treatment.

The following will be considered a dose-limiting toxicity:

- Grade 4 neutropenia and thrombocytopenia ≥ 7 days (absolute granulocyte count $< 0.5 \times 10^9/L$)

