17.2 Adverse Events

Adverse Events will be reported as indicated by the appropriate following table (see below).

Definition

An adverse event is defined as any untoward or unfavorable medical occurrence in a human research study participant, including any abnormal sign (for example, abnormal physical exam or laboratory finding), symptom, clinical event, or disease, that occurs during the subject's participation in the research, whether or not it is considered related to the subject's participation in the research.

Adverse events encompass clinical, physical and psychological harms. Adverse events occur most commonly in the context of biomedical research, although on occasion, they can occur in the context of social and behavioral research. Adverse events may be expected or unexpected.

Severity

Adverse events will be graded by a numerical score according to the defined NCI Common Terminology Criteria for Adverse Events (NCI CTCAE) and version number specified in the protocol. Adverse events not specifically defined in the NCI CTCAE will be scored on the Adverse Event log according to the general guidelines provided by the NCI CTCAE and as outlined below.

- Grade 1: Mild
- Grade 2: Moderate
- Grade 3: Severe or medically significant but not immediately life threatening
- Grade 4: Life threatening consequences
- Grade 5: Death related to the adverse event

Serious Adverse Events

ICH Guideline E2A and the UTSW IRB define serious adverse events as those events, occurring at any dose, which meets any of the following criteria:

- Results in death
- Immediately life-threatening
- Results in inpatient hospitalization or prolongation of existing hospitalization
- Results in persistent or significant disability/incapacity
- Results in a congenital anomaly/birth defect
- Based upon appropriate medical judgment, may jeopardize the subject's health and may require medical or surgical intervention to prevent one of the other outcomes listed in this definition.

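### Section 15.2 does not separate on-treatment adverse events from those in the year after exit, and its separate severe-event line stops at grade 4

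*Combined protocol and SAP*

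**What the plan says.** The safety summary is set out in Section 15.2. The analysis set is everyone dosed: "The safety analyses will be performed on all patients who receive any dose of therapy". Frequency and severity of all adverse events are to be described by body system, and causality is noted. A further line is added: "frequency of Grade 3 or 4 adverse events will be described separately". Serious adverse events are summarized with a causality assessment. On timing, the section says only "Adverse events will be recorded for up to 1 year following discontinuation from study". It defines no on-treatment or treatment-emergent period.

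Two other sections describe the period differently. Section 11.0, for Phase I, says "The patients will be followed for thirty days following the end of the first cycle for adverse events", and adds "During this thirty-day period and beyond patients will be administered sorafenib at the discretion of the treating oncologist". Section 17.2 defines an adverse event as one "that occurs during the subject's participation in the research, whether or not it is considered related to the subject's participation in the research".

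On grading, Section 17.2 runs from grade 1 to grade 5, with grade 5 being death related to the event. The dose-limiting-toxicity rule in Section 11.0 counts non-hematologic events of grade 3 and above.

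**The concern.** A secondary objective is the safety and tolerability of the combination. The trial has one arm, so the reported event rates are the whole of the evidence on it. If the table takes in everything recorded up to a year after exit, it covers time when the patient is no longer on protocol treatment, may have progressed and may be on other therapy. No comparator shows how much of the rate is background. The protocol recognises the background problem in Section 11.0: it restricts non-hematologic dose-limiting toxicities to definite or probable attribution, because over 50% of placebo patients in the cited phase III sorafenib trial had events of grade 3 or higher. Section 15.2 carries no equivalent rule.

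The separate severe line has the opposite fault. It stops at grade 4, so the figure most likely to be quoted as the severe toxicity rate leaves out the worst events. Section 3.2.4 gives reason to expect some: an earlier bavituximab study in lung cancer reported fatal drug-related events in three of 49 patients.

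**Working it through.** **The plan's own figure.** The safety summary states none. The Phase II size of 38, used below, does reproduce with a one-sample exponential test on the cube-root scale:
- Events = [(1.645 + 0.842) / (3 × ((8.3/5.5)^(1/3) − 1))]² = 31.8.
- The probability of an event at a median of 8.3 months, with 24 months of uniform accrual and 12 of follow-up, is 0.8415.
- 31.8 / 0.8415 = 37.8, or 38.

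Nothing below depends on this derivation.

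**Share of observation time after exit, Phase II.** Inputs from the documents: median time to progression 5.5 or 8.3 months (Section 15.1), sorafenib median overall survival 10.7 months (Section 3.1), and the 12-month post-exit window (Section 15.2). Assumptions not in the documents: exponential times, treatment until progression, and a post-exit survival median between 5.2 months (10.7 − 5.5, a rough difference of medians) and 10.7 months.

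- Mean time on treatment = median / ln 2: 5.5/0.693 = 7.93 months; 8.3/0.693 = 11.97 months.
- Mean post-exit time, capped at 12 months = (r / ln 2) × (1 − 0.5^(12/r)). For r = 5.2 this is 7.50 × 0.798 = 5.99 months; for r = 10.7 it is 15.44 × 0.540 = 8.34 months.
- Share = post-exit / (post-exit + on treatment):

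| Time to progression, median | Post-exit median 5.2 | Post-exit median 10.7 | All survive the 12 months |
|---|---|---|---|
| 5.5 months | 5.99/13.92 = 43% | 8.34/16.27 = 51% | 12/19.93 = 60% |
| 8.3 months | 5.99/17.96 = 33% | 8.34/20.31 = 41% | 12/23.97 = 50% |

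**Phase I.** Treatment lasts 28 days = 0.92 months. If the one-year window applies and every patient is observed throughout, the share is 12/(12 + 0.92) = 93%.

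**With a 30-day window instead.** Phase II: 0.99/(0.99 + 11.97) = 8% to 0.99/(0.99 + 7.93) = 11%. Phase I: 30/(28 + 30) = 52%, although sorafenib may continue during those thirty days.

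**Fatal events and the severe line.** The lung cancer study gives 3/49 = 6.1%. If that rate held for 38 patients, the expected number is 38 × 3/49 = 2.3, and the chance of at least one is 1 − (46/49)^38 = 91%. None would count in a line limited to grades 3 and 4.

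**Phase I in the denominator.** Section 1.0 expects 9–18 Phase I and 38 Phase II patients. Phase I would be 9/47 = 19% to 18/56 = 32% of everyone dosed.

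**The case against.** The best defence is that Section 15.2 says later events are recorded, not that they are pooled into the main table. The section describes all events by severity, notes causality and summarizes serious events with causality, so an analyst could separate related events. Longer collection is conservative, and the data and safety monitoring committee reviews serious events as they are reported. Section 11.0's thirty days may simply serve the Phase I safety review, and participation in Section 17.2 could be read to include follow-up. All of this is fair. But pooling is what results when a plan gives no window, and no rule says how causality is to be used in the tables.

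A reader might go further in three ways that the documents do not support:

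- *That post-exit events swamp the regimen's rates, or that nearly every patient would show a severe event.* The documents give no post-exit adverse-event rate. One can compute 1 − 0.5^(12/5.2) = 80% dying within the window, but that is an estimate of deaths, not of adverse events. It rests on subtracting two medians and falls to 54% with a post-exit median of 10.7 months. In Phase II, post-exit time is material but not clearly dominant. Nor would a time window remove the over-50% placebo rate, since background disease acts during treatment too; that is a matter for attribution.
- *That deaths disappear from the safety report.* The sentence reads "In addition, frequency of Grade 3 or 4 adverse events will be described separately": the line is an addition. Grade 5 events remain in the all-severity description, and death is a criterion for a serious event. In the lung cancer study the fatal events were likewise reported under serious events, beside a separate grade 3–4 rate. Death from progression is also not automatically grade 5.
- *That the plan orders one denominator for both phases.* Section 1.0 places the secondary safety aim in the Phase II setting, and Phase I is judged cohort by cohort. Section 15.2 is silent on the layout; it does not require pooling.

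**Conclusion.** The concern holds in a limited form. Section 15.2 leaves the adverse-event period for analysis undefined while recording events for a year after exit, and Sections 11.0 and 17.2 describe other periods. Read as written, post-exit time is about 33–60% of Phase II adverse-event observation. It is about 93% in Phase I if the one-year window applies there. These shares depend on exponential times, treatment until progression and the assumed post-exit survival; they are shares of time, not of events. In a single-arm trial that is enough to blur the rates attributed to the regimen.

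Separately, the severe line omits grade 5. About 2.3 such events would be expected among 38 patients if the lung cancer study's rate carried over; that study combined bavituximab with chemotherapy in another disease, so the figure only indicates scale. The effect is on the headline severe rate, not on whether deaths are reported. The primary endpoint is untouched. The change is worth making because it alters the reported safety rates and costs almost nothing.

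**What to change.** In Section 15.2:

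1. Reconcile the periods in Sections 11.0, 15.2 and 17.2. Let the main adverse-event table run from first dose to 30 days after the end of protocol study treatment. For Phase I that means the end of cycle 1, which is where Section 11.0's thirty days start. That count does not run from the last dose of either drug, and a last-dose cut-off would keep Phase I events in the main table for as long as sorafenib continues afterwards. Put later events, up to one year, in a second table, and show causality in both.
2. Change the severe line to grade 3 or higher, with grade 5 on its own line.
3. Show Phase I by dose level, apart from Phase II, in keeping with the Phase II safety aim in Section 1.0.

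The cost is extra table columns and a fixed cut-off that moves some late related events to the second table, where the causality column keeps them visible. Data collection for one year does not change.

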6.0 CRITERIA FOR SUBJECT ELIGIBILITY

6.1 Subject Inclusion Criteria

1. Patients must have a diagnosis of hepatocellular carcinoma by at least one criterion listed below:
 - a. Histologically confirmed hepatocellular carcinoma
 - b. Axial imaging consistent with liver cirrhosis and at least one solid liver lesion ≥ 2 cm with early enhancement and delayed enhancement washout regardless of alpha-fetoprotein (AFP) levels.
 - c. AFP ≥ 400 ng/ml and evidence of at least one solid liver lesion ≥ 2 cm regardless of specific imaging characteristics.
2. Locally advanced or metastatic disease.
 - a. Patients with locally advanced disease must have disease deemed to be unresectable or not eligible for hepatic transplantation surgical oncologist or transplant physician.
 - b. Measurable disease, as defined as lesions that can accurately be measured in at least one dimension (longest diameter to be

measured) according to Response Evaluation Criteria in Solid Tumors (RECIST, version 1.1) at least 2 cm with conventional techniques or at least 1 cm with spiral computed tomography.

3. Child-Pugh Score A or B7.
4. Age \geq 18 years.
5. Eastern Cooperative Oncology Group (ECOG) Performance Score of 0-2.
6. Absolute neutrophil count \geq 1,200 cells/mm³.
7. Platelet count \geq 70,000 cells/mm³.
8. Total bilirubin \leq 3.0 mg/dl.
9. Hemoglobin \geq 8.5 g/dl.
10. INR \leq 1.8 (therapeutic anticoagulation allowed as long as medically indicated.)
11. Creatinine \leq 1.5 times upper limit of normal.
12. Women of childbearing potential must have a negative pregnancy test.
13. No clinically significant episode of gastrointestinal bleeding within the previous 30 days.
14. Men and women of childbearing potential must be willing to consent to using effective contraception while on treatment and for at least 3 months thereafter.
15. At least 4 weeks since prior locoregional therapy including surgical resection, radiotherapy, hepatic arterial embolization or chemoembolization, radiofrequency ablation, percutaneous injection or cryoablation (treatment of target lesion only, non-target lesions can be treated with locoregional therapy). Provided the target lesion increased in size by 25% or more or the target lesion was not treated with locoregional therapy.
16. Greater than 4 weeks since prior interferon therapy.
17. Greater than 4 weeks since prior and no concurrent use of rifampin or St John's wort.
18. Prior antiviral therapy is allowed.
19. Life expectancy $>$ 12 weeks.

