8.2 Phase II component

To be completed within 30 +/-5 days of starting therapy:

- CT or MRI abdomen with liver protocol
- A 12 lead electrocardiogram
- Biopsy (US or CT guided) of malignancy with histologic confirmation
- Bilateral venous duplex of lower extremities
- Documentation of all measurable or non-measurable disease parameters including radiographic imaging procedures within four weeks of study entry, and measure of biochemical marker of disease (if applicable) within four weeks of study entry. The RECIST criteria as defined by CTEP (<http://ctep.info.nih.gov/policies>) define measurable and non-measurable disease.
- Signed informed consent for study participation.

To be completed within 14 +/- 5 days of starting therapy:

- History and physical examination, including height, weight, calculated body surface area (BSA), vital signs (temperature, pulse rate, respiration rate, blood pressure), and performance status (ECOG). See Appendix A for ECOG scale.
- Serum pregnancy test for all women of childbearing potential within 14 days of starting therapy. If the test result is positive, the patient will not be allowed to participate in the study.
- Laboratory evaluation and coagulation parameters
 - CBC with differential and platelet count
 - Serum chemistries (Na, Cl, BUN, Creatinine, K, bicarbonate and glucose), albumin and calcium
 - Liver function tests (AST, ALT, alkaline phosphatase, total bilirubin),
 - Coagulation parameters (aPTT, PT and INR)
 - Urinalysis, record protein, glucose and blood
 - Alfa-fetoprotein
 - Viral hepatitis titers
- Recording of concomitant medications

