- platelet count $< 25,000$
- ALT or AST levels \geq grade 3 adverse event for 7 days
- \geq grade 3 adverse event for any non-hematologic toxicity (excluding alopecia and non-premedicated nausea/vomiting) attributable to drug therapy by the definition of definite or probable and not possibly. In the SHARP trial patients in the placebo arm had over a 50% \geq grade 3 adverse event rate due to the comorbidities seen in the patient population with advanced HCC.

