15.0 BIOSTATISTICS

The study is an open-label, non-randomized single-arm, single institution phase I/II therapeutic clinical trial. The study population will be patients with advanced hepatocellular carcinoma.

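### Section 15.2 grades laboratory results without a baseline reference, so tests with no entry limit (chiefly AST/ALT) could show grade 3-4 values that were already present at entry

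*Combined protocol and SAP*

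**What the plan says.** Section 15.2 (Secondary endpoints) gives the whole plan for laboratory safety: "Laboratory assessments will also be described according to the NCI CTCAE v 4 criteria, with separate descriptions for Grade 3 or 4 laboratory abnormalities". It then adds "Clinically significant laboratory abnormalities will be described as well", without defining clinical significance. The analysis set is broad: "The safety analyses will be performed on all patients who receive any dose of therapy". In the paragraph on adverse events it says "Causality will also be noted", and serious adverse events get a causality assessment. No causality step is stated for laboratory grades.

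Section 15.0 describes the design: "The study is an open-label, non-randomized single-arm, single institution phase I/II therapeutic clinical trial".

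Section 8.2 lists the phase II screening tests, among them "Liver function tests (AST, ALT, alkaline phosphatase, total bilirubin", together with albumin, calcium, serum chemistries, blood counts and coagulation tests. Section 9.2 repeats the screening laboratory and coagulation tests before each cycle. The table in Section 10.0 adds blood counts, liver tests and coagulation tests at each bavituximab dose.

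Section 6.1 admits patients with "Child-Pugh Score A or B7" and sets numerical limits for six laboratory tests only.

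**The concern.** A summary by raw grade records how abnormal a value is, not whether it changed after treatment began. In a randomized trial the control arm would show the background. This trial has none: the sorafenib-alone patients mentioned in Section 10.1 supply tissue and blood for correlative work, and Section 15.2 plans no safety comparison with them.

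Safety and tolerability of the combination is a stated secondary objective (Section 2.0). If patients with advanced disease enter with a grade 3-4 value in some test, they remain grade 3-4 at the first on-study draw unless they improve, and the planned line can count them. A reader could not then divide the count into values brought in and values that worsened. Transaminases matter most, because they have no entry limit and Section 11.0 itself treats raised ALT or AST as a sign of toxicity.

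**Working it through.** The plan attaches no figure to this point, so there is nothing to reproduce. The check has three steps.

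**1. Does any other section supply a baseline rule?** The definition of an adverse event in Section 17.2 covers abnormal laboratory findings that arise during participation, but has no condition that the finding be new or worse than before. Sections 8, 9.2 and 10.0 say when tests are drawn, not how they are compared. No section defines a baseline for laboratory analysis.

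**2. For which tests is grade 3 possible at entry?** The entry limits come from Section 6.1, and Section 9.2 repeats all but INR for the first day of cycle 1. The documents do not print the CTCAE grade 3 boundaries, so those below are assumptions, as are the upper limits of normal (ULN).

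| Test | Worst value admitted | Assumed grade 3 boundary |
|---|---|---|
| Neutrophils | 1,200/mm³ | < 1,000/mm³ |
| Platelets | 70,000/mm³ | < 50,000/mm³ |
| Hemoglobin | 8.5 g/dl | < 8 g/dl |
| Bilirubin | 3.0 mg/dl = 2.3 to 3.0 × ULN (ULN 1.3 to 1.0) | > 3 × ULN |
| INR | 1.8 = 1.5 to 1.8 × ULN (ULN 1.2 to 1.0) | > 2.5 × ULN |
| Creatinine | 1.5 × ULN | > 3 × ULN |
| AST, ALT | no limit | > 5 × ULN |
| Alkaline phosphatase, aPTT, electrolytes | no limit | not needed: any grade is admitted |

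The six limited tests do not reach grade 3 at entry under these assumptions. A later grade 3-4 value in one of them is already a worsening, and only the grade 1-2 counts can include entry abnormalities. Bilirubin is the closest: at a ULN of 1.0 mg/dl it sits on the boundary without crossing it. The INR row takes the limit to apply to anticoagulated patients as well; the bracketed remark in Section 6.1 could be read otherwise.

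For tests without a limit, a patient may enter at grade 3 or above and be counted.

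**3. How many patients could that be?** Let q be the proportion entering at grade 3 or above in one such test. The documents give no value, so a range is assumed. With 38 phase II patients (Section 15.1), the expected carry-in is 38q, and the chance of at least one such patient is 1 − (1 − q)^38.

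| Assumed q | 38q | Chance of at least one |
|---|---|---|
| 2% | 0.8 | 54% |
| 5% | 1.9 | 86% |
| 10% | 3.8 | 98% |
| 20% | 7.6 | > 99.9% |

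As an illustration, four carried-in patients would be reported as 4/38 = 10.5% (exact 95% CI 2.9% to 24.8%) even if nobody worsened. If the count is restricted to patients whose grade rose from the last pre-dose value, the carry-in is zero by construction.

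**The case against.** The strongest reply is that Section 15.2 is silent rather than wrong. It does not say that pre-dose values enter the summary, it does not attribute laboratory grades to the treatment, and nothing in it prevents a shift table. The summary is descriptive, with no test, threshold or stopping rule attached, and the tests most often watched for toxicity are limited at entry. All of this stands, and it is why the point is minor. It does not remove the gap: followed as written, the text gives the analyst no rule for separating values present at entry from values that worsened.

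Three stronger readings are tempting but not supported.

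- A reader might infer that entry abnormalities are in fact counted as grade 3-4 findings of the combination. The text permits such counting but does not state it, and for the six limited tests it would not arise at grade 3-4 under the assumed cut-offs.
- A reader might take the Section 11.0 remark about placebo patients in the earlier sorafenib trial, an "adverse event rate due to the comorbidities seen in the patient population with advanced HCC", as a measure of laboratory background. That figure, over 50% at grade 3 or above, covers adverse events overall. It is neither a laboratory rate nor a rate at entry.
- A reader might call the whole population cirrhotic. Section 6.1 requires cirrhosis on only one of its three diagnostic routes, and Section 4.2.2 rests phase II eligibility on histology.

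It is also fair to object that a baseline reference cannot fully separate disease from drug. Liver disease and cancer may progress on study, and Sections 3.2.3 and 12.2 ascribe aPTT prolongation under bavituximab to assay interference. A shift table would still show both as worsening.

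**Conclusion.** The concern holds in limited form. Laboratory grades are to be described without a baseline reference in a single-arm trial, so for tests with no entry limit the grade 3-4 line could include patients who did not worsen. AST and ALT are the main case. For the six limited tests the effect stops at grades 1-2.

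The size cannot be derived from the documents. The range of 0.8 to 7.6 of 38 patients per test rests wholly on an assumed 2-20% prevalence at entry, and the division between limited and unlimited tests rests on the assumed grade boundaries and ULNs above. The primary endpoint, the sample size and every stated decision are unaffected. Severity is minor: a cheap improvement to a secondary descriptive summary.

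**What to change.** Keep the CTCAE v4 sentence in Section 15.2 and add after it:

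> For each laboratory test, a shift table of baseline grade (last value before the first dose of study therapy) by worst on-treatment grade will be given. Grade 3-4 abnormalities will be reported both for all patients and for patients whose grade rose from baseline, with the number already at grade 3-4 at baseline shown.

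The team should also state when the on-treatment period ends for this table, since Section 15.2 records adverse events for up to a year after discontinuation.

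The cost is one extra table per test. No new samples, visits or patients are needed, because screening and on-study values are already collected. There are two limits. The grade-rise count misses a patient who deteriorates within the same grade, which is why both counts are shown. A rise from baseline may still reflect disease progression or, for aPTT, assay interference, so the table should be described as showing change on study and not drug effect.
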